1.7 Drugs/Devices/Biologics

N/A.

1.8 Specimen Collection

N/A.

1.9 Data Collection

A. Primary Data Collection

- **Location:** This project will be conducted at the Rutgers University Affective and Biological Underpinnings of Substance Use and Anxiety (ABUSA) Laboratory located on the 2nd floor of [name]. The lab space is equipped with two rooms for psychophysiological assessment with adjacent rooms for monitoring, an in-lab smoking room that is ventilated to the outdoors with an adjacent control room for monitoring. Some eligibility and baseline assessments will be conducted remotely, using video-conferencing software (e.g., HIPAA compliant Zoom or Teams platforms) and online survey collection software (e.g., Qualtrics).
- **Process of Data Collection:** Data will be collected by IRB-approved and trained research staff from both labs of the Principal Investigators, in accordance with the procedures described in detail in section 1.3. In brief, combustible cigarettes smokers with emotional distress (N=88) will be randomized to receive puff topography biofeedback (n = 44, 50%) or sham training (n = 44, 50%) prior to exposure to a laboratory stressor paradigm. Stress-precipitated smoking behavior will be assessed directly after the stressor task, wherein participants will be given the instructions to smoke utilizing their assigned puff training. Smoking reinforcement will be measured using a multi-method approach, including self-report, psychophysiology, and behavioral indices
- **Timing and Frequency:** After the initial telephone screening, data collection will occur on one remote occasion and two in-person occasions. The remote session entails one initial assessment to confirm eligibility and collection of baseline data via interview and self-report. For the in-person visits, V1 entails data collection through self-report measures (administered at the starred time points in **Figure 3**), as well as receiving their assigned training condition. V2 will occur on the following day at the same time as V1.
- **Procedures for Audio/Visual Recording:** The diagnostic interview during the remote session will be recorded via HIPAA compliant platform (e.g., Zoom, Teams) to be used for supervision purposes as well as to ensure diagnostic fidelity.
- **Study Instruments:** **Puff topography** will be objectively measured with the *CreSS micro* (Plowshare Technologies, Borgwaldt KC, Inc), a hand-held device that has a sterilized flow meter mouthpiece that is

connected to a pressure transducer, which converts pressure into a digital signal that is sampled at 1,000Hz. Puff indices will be averaged and examined at puff-to-puff level. To index changes in **CVC** as a function of condition, continuous ECG and respiration data will be sampled at 1,000Hz, and differences in RSA from the 5-min adaptation period (V1) to the 5-min peri-smoking period (V2) will be derived and scored using cardiopro in accord with established guidelines.⁷³ **Smoking reinforcement** will be assessed with: **(a)** the *Short-Cigarette Purchase Task* (S-CPT),⁷⁴ a hypothetical purchase task designed for repeated assessment of cigarette (wanting), modified to purchasing of the “last cigarette smoked” to index intensity (*consumption when free*), O_{max} (*maximum expenditure on cigarettes*), and breakpoint (*point at which consumption is zero*) and **(b)** the *Modified Cigarette Evaluation Questionnaire* (mCEQ),⁷⁵ which assesses how respondents feel about the “last cigarette smoked” with subscales that tap liking (*cigarette satisfaction*), wanting (*craving reduction*), and learning (*psychological reward*).

▪ **Subject Identifiers:**

Data will be de-identified with an arbitrary ID number. Subject identifiers of name, email address, address, and phone number will be stored under lock and key and in password-protected electronic databases, separate from all data.

B. Secondary Data Collection

Additional measures administered and administration time points are included below in **Table 1**. Please refer to **Figure 3** for where these time points fall in the visit procedures. Full measures are attached for review.

Measure	Screening	Baseline (remote session)	0	Adaptation	1 1a, and 1b	Smoking	2	Rest
Phone Screen.	X							
Depression, Anxiety, and Stress Scales, 21 Item Version (DASS-21).		X						
The Mini International Neuropsychiatric Interview 7.0.0 (MINI) sections C, I, J, and K.		X						
Demographic information.		X						
Smoking History Questionnaire.		X						
Medical History Form.		X						
McCarthur Ladder for Subjective Social Status.		X						
Economic Strain Questionnaire.		X						
Fagerstrom Test for Cigarette Dependence.		X						

Mood and Anxiety Symptoms Questionnaire.		X					
Multidimensional Experiential Avoidance Questionnaire.		X					
Anxiety Sensitivity Index.		X					
Distress Tolerance Scale.		X					
Distress Intolerance Index.		X					
Brief WISDM.		X					
Positive And Negative Affect Schedules (PANAS).		X					
Pittsburgh Sleep Quality Index.		X					
Readiness to Quit.		X					
Difficulties in Emotion Regulation Scale.		X					
Avoidance and Inflexibility Scale.		X					
Pre-Session Review Sheet			X				
Modified Cigarette Evaluation Questionnaire.							X
Hypothetical Cigarette Purchase Task.		X		X			X
Visual Analogue Scales of Discrete Affective States.			X		X		X
Brief Questionnaire of Smoking Urges.			X		X		X
State Difficulties in Emotion Regulation Scale – modulation subscale.					X (not 1a)		
Expired CO.			X				X
CReSS topography.						X	
Psychophysiological parameters (e.g., RSA, BVP, Respiration).				X		X	X

2.2 Research Staff Training

All research personnel will receive, if they have not already, extensive (10-15 hours) training on all study procedures. PIs [name] and [name] will oversee training, which will include verbal description and behavioral demonstration. Staff will then be led through the study's procedures as mock participants, before administering each study task to the PIs or graduate students designated by the PIs to allow for sufficient practice and corrective feedback if necessary. All study staff have previously administered some or all of the aforementioned techniques during prior investigations.

2.3 Resources Available

Research will take place in the Affective and Biological Underpinnings of Substance Use and Anxiety (ABUSA) laboratory in the Department of Psychology on the second floor of [name]. These facilities include the materials necessary for data collection (e.g., carbon monoxide smokerlyzer, physiological monitoring) and secure storage (e.g., locked file cabinets, password-secure computers).

3.0 Multi-Center Research

N/A.

4.0 Subject Considerations

4.1 Subject Selection and Enrollment Considerations

A. Method to Identify Potential Subjects

Participants will be recruited through: (a) free online internet advertisement (e.g., Facebook posts, Craigslist), (b) flyers posted in the community and health-related clinics in the New Brunswick and Central New Jersey area, and (c) paid advertisements through BUMP Digital Marketing and Build Clinical, both online recruitment services used in previous research by both PIs. BUMP and Build Clinical will target daily smokers in the Northern and Central New Jersey areas via targeted advertisements on Facebook, Instagram and other social media sites and websites. Recruitment materials are attached. Any individuals meeting inclusion/exclusion criteria will be provided the opportunity to participate in this study. Individuals interested in participation will undergo a brief phone screen to determine presence of inclusion criteria and absence of exclusion criteria.

B. Recruitment Details

We intend to recruit 180 daily smokers and retain 80 eligible. The study will be conducted at the Affective and Biological Underpinnings of Substance Use and Anxiety (ABUSA) laboratory at Rutgers University, in New Brunswick, NJ. The ABUSA laboratory (directed by MPI [name]) has a psychophysiological suite and ventilated in-laboratory smoking room. Through our studies (R03DA041556; F31DA024919; R21DA045182; R34DA043751), we have developed effective

strategies to recruit emotionally-distressed smokers from the community at a consistent rate. We will recruit via community fliers and announcements, local tobacco clinics (via Co-Is [name]/[name]), and both BUMP digital marketing and Build Clinical, online recruitment services.

Subject Screening

Potential participants will be screened via telephone by protocol-approved research staff, trained under the direction of Drs. [name] and [name]. See section 11.0 Recruitment Materials for the full text of the phone screen.

- **Inclusion Criteria**
 - (1) Age 18-55; (2) daily smoking \geq 8 cigarettes/day verified by carbon monoxide analysis of breath sample \geq 5 ppm;⁶⁴ (3) smoking within 30 min of waking; and (4) English fluency.
- **Exclusion Criteria**
 - (1) current smoking cessation treatment; (2) past-month reduction of cigarettes/day by \geq 50%; (3) non-nicotine substance use disorder (moderate or severe); (4) past-year psychiatric instability (e.g., psychosis, mania); (5) severe visual, hearing, or cognitive impairments; (6) medical condition that could impact stress reactivity or physiology (e.g., respiratory, cardiovascular, autoimmune, pregnancy, neurodegenerative disorders); and (7) current regular use of medication that could affect CVC (e.g., beta blockers, benzodiazepines; note-use of SSRIs/SNRIs is permitted if dose is stable \geq 6 wks).

4.2 Secondary Subjects

N/A.

4.3 Number of Subjects

A. Total Number of Subjects

80 total participants are expected to complete the full protocol. In order to have 80 full completers (attendees that remain eligible and complete both visits), 180 are expected to be initially enrolled.

B. Total Number of Subjects If Multicenter Study

N/A.

C. Feasibility

Based on our prior trials, we expect to retain 90% of subjects across the two visits. Financial incentives will also aid in retention: with \$20 for completing the remote screening/baseline visit, \$30 for completing V1 and \$100 for completing V2. We have used this back-loaded schedule of compensation in our prior smoking lab-studies with high retention rates (F31DA024919; F31DA035564). Additionally, with the use of Build Clinical and BUMP Digital Marketing, we expect to be able to consent and enroll 80 completers very feasibly. Prior engagement through both labs with BUMP's recruitment service has yielded up to 12 inquiries per day in prior smoking research, and the eligibility criteria would allow a broad scope of potential participants.

4.4 Consent Procedures

A. Consent Process

- **Location of Consent Process**

The initial consent process will take place via video conferencing software during the initial remote visit. Consent to the TSST procedures will occur in the laboratory at [name] at the start of V2.

- **Ongoing Consent**

Ongoing consent will be confirmed on the basis of ongoing communication and study participation. In addition, participants will explicitly be reminded of study expectations, limitations, compensation, and right to withdraw. Study staff will attempt to contact participants who miss study appointments or follow-up appointments until they provide verbal or written indication that they no longer wish to participate.

- **Individual Roles for Researchers Involved in Consent**

All of the research assistants, graduate students, and project manager have been trained and are experienced in prior consent administration and may collect consent from participants through the course of the protocol.

- **Consent Discussion Duration**

Staff will go over details regarding the procedure, time commitment, payment, risks/benefits, and option to discontinue the study at any time without penalty. We anticipate that it will take participants 5 minutes to read the consent and up to an additional 5 for staff to review relevant information.

- **Coercion or Undue Influence**

During the consent process, staff will make clear to participants that they will receive full compensation if eligible, and that early termination will result in payment for the portion completed, as detailed in the consent, and will not result in loss of ability to participate in future research.

Subject Understanding

Participants will be asked if they require any clarification and must verbally indicate they fully understand all study procedures, in addition to providing written consent.

B. Waiver or Alteration of Consent Process

N/A.

C. Documentation of Consent

- **Documenting Consent**

All participants will sign the consent form, indicating their consent.

- **Waiver of Documentation Of Consent (i.e., will not obtain subject's signature)**

N/A.

4.5 Special Consent/Populations

N/A.

4.6 Economic Burden and/or Compensation for Subjects

A. Expenses

Participants may incur costs of transportation to arrive at the study site. Travel and transportation costs will not be reimbursed.

B. Compensation/Incentives

Participants will receive compensation in cash. Participants will receive compensation based on study attendance and continued eligibility. They will receive \$30 for the remote screening/baseline session. If eligible to continue, they will receive an additional \$70 upon completion of V1. If they return for V2, participants will receive \$100 for participating in V2 and a \$50 completion bonus. Compensation totals a potential of up to \$250 per participant.

C. Compensation Documentation

Participants will sign receipts indicating their receipt of compensation. Compensation will also be logged electronically in a tracking log accessible only to research staff.

4.7 Risks of Harm/Potential for Benefits to Subjects

A. Description of Risks of Harm to Subjects

(1) *Phone Screen and Questionnaire Completion*: Potential participants may become uncomfortable or distressed when asked certain questions (e.g., regarding illicit substance use; current/past mental health and physical health). However, Drs. [name] and [name] have many years of experience administering these questionnaires in various study protocols and study personnel will receive extensive training in conducting the Phone Screen. Also, participants will be offered an additional layer of protection via a Certificate of Confidentiality.

(2) *PTBT*: There are some minimal risks associated with the administration of the proposed breathing interventions. The most often observed risk is discomfort breathing at a pace that is much slower than typical and worry that one is not inhaling adequate air. To address this potential risk, study clinicians will be carefully trained in providing participants with a clear rationale for the procedure, clinical management of distress associated with the intervention, and appropriate adjustments to ensure participants are able to adhere to the protocol.

(3) *Physiological Recording*: All of our sensors record responses from the surface of the body and are hence noninvasive and should not cause the participants any discomfort or physical harm. Patients may experience mild discomfort with the application and removal of passive electrodes to monitor their physiological parameters. However, we do not anticipate this discomfort to be longstanding. To minimize discomfort, all sensors are placed and removed by study staff that will receive training in appropriate placement and removal.

(4) *Assessment Procedures*: No risks are associated with self-report or behavioral assessments other than mild distress due to the sensitive nature of questions or induced distress as a function of difficulty or attention demands on some of the behavioral tasks. Study personnel are experienced and sensitive to this issue and will cease testing if a participant displays excessive frustration during behavioral testing, although neither PI has experienced this in her prior research.

B. Procedures which Risk Harm to Embryo, Fetus, and/or Pregnant Subjects

N/A.

C. Risks of Harm to Non-Subjects

N/A.

D. Assessment of Social Behavior Considerations

No risks are associated with self-report or behavioral assessments other than mild distress due to the sensitive nature of questions or induced distress as a function of difficulty or attention demands on some of the behavioral tasks. Study personnel are experienced and sensitive to this issue and will cease testing if a participant displays excessive frustration during behavioral testing, although the PI has never experienced this in her prior research.

E. Minimizing Risks of Harm

Described above in section A and D.

▪ **Certificate of Confidentiality**

This research is covered by a Certificate of Confidentiality. Researchers with this Certificate may not disclose or use information or documents that may identify study participants in any federal, state, or local civil, criminal, administrative, legislative, or other action, suit, or proceeding, or be used as evidence, for example, if there is a court subpoena, unless study participants have consented for this use. Information or documents protected by this Certificate cannot be disclosed to anyone else who is not connected with the research except, if there is a federal, state, or local law that requires disclosure (such as to report child

abuse or communicable diseases but not for federal, state, or local civil, criminal, administrative, legislative, or other proceedings, see below); if participants have consented to the disclosure, including for their medical treatment; or if it is used for other scientific research, as allowed by federal regulations protecting research subjects. A Certificate of Confidentiality does not prevent participants from voluntarily releasing information about themselves or their involvement in this research. If a participant wants their research information released to an insurer, medical care provider, or any other person not connected with the research, they must provide consent to allow the researchers to release it. The Certificate of Confidentiality will not be used to prevent disclosure as required by federal, state, or local law of harm to self or others as well as reports of child and elderly abuse and neglect.

▪ **Provisions to Protect the Privacy Interests of Subjects**

Our research team employs standard procedures to ensure confidential information about study participation is not disclosed. All data are linked to an arbitrary study ID unrelated to personal information. The file linking participants to their study ID will be stored in a password-protected file, located within a password-protected database on an encrypted computer and maintained separately from de-identified personal data files. Only select trained laboratory personnel will have access to the file. All computer files or printed data used for analysis also will be de-identified. Consent forms and payment forms will be stored in a locked file cabinet separate from data in an office that is locked when not occupied. Participants' confidentiality also is protected by never associating a participant's name with results in any published or otherwise publicly presented report. Demographic information, including information about participants' age, ethnicity, education, marital status and employment status, will be reported using averages and percentages computed over multiple participants and never reported at the level of individual participants.

F. Potential Benefits to Subjects

While no individual benefits for subjects are anticipated, the data obtained through this study may help inform and shape effective interventions for smoking cessation.

5.1 Health Insurance Portability and Accountability Act (HIPAA)

N/A.

5.2 Family Educational Rights and Privacy Act (FERPA)

N/A.

5.3 Code of Federal Regulations Title 45 Part 46 (Vulnerable Populations)

A. Special Populations

N/A.

5.4 General Data Protection Regulation (GDPR)

N/A.

5.5 NJ Access to Medical Research Act (Surrogate Consent)

N/A.

6.0 Data Management Plan

6.1 Data Analysis

Interventional Research Protocol Template (HRP-503a) 2.4.20

PI: [name].; [name].

Protocol Title: Puff Topography Biofeedback on Smoking

Reinforcement

Protocol Version Date: 2020000645 v.21 05/02/2023

Prior to conducting outcome analyses, we will use descriptive statistics and graphical analysis to evaluate the distributional properties of outcome variables. T-tests and χ^2 initial analysis will be used to evaluate the equivalence of the groups on baseline variables (i.e., successful randomization).

Test of Aim 1: First, tests of the effects of puff training on puff topography indices (i.e., puff volumes and duration, and inter-puff intervals) will be conducted using linear regression models. The mean level of each index over the course of the stress-precipitated smoking session will be calculated for each individual to be used as outcomes. The primary independent variable is training group (PTBT vs. Control). Planned covariates include biological sex (0=male, 1=female), number of cigarettes per day, and emotional distress (DASS-21), and the models will be tested with and without covariates. Effect size (d) will also be calculated. In addition, a series of multilevel models will be used to test whether 1) the mean levels and 2) changes in the levels of puff topography (i.e., volume, duration, inter-puff intervals) during stress-precipitated smoking session differ across groups. Levels of puff volumes, durations, and inter-puff intervals for each puff (outcomes), and puff number (level 1) make up the first level of data nested within individuals at the second level. Training group and other baseline characteristics will be entered in the models as level 2 variables. We will examine the effects of PTBT (vs. Control) on the individual mean (i.e., the middle point of the values over time) and the individual trajectory slope (i.e., the rates of changes over time) for each topography index in separate models. A cross-level interaction term between training group (level 2) and puff number (level 1) will be included in each model. Puff number will be centered around the mid-point for each individual so that the intercept reflects the estimated mean level of each topography outcome. Separate quadratic and cubic slopes (squared and cubic puff number) will be included as level 1 predictors if their inclusion improves model fit. Intercepts and slopes will be specified as random if it improves model fit and coefficients varied significantly across individuals. Deviance statistics will be used to compare model fit between two models.⁷⁹ Unconditional models will be initially estimated, and then training group will be included as a level-2 variable predicting level-1 intercept and slope coefficients. The models will be fitted with and without level 2 planned covariates (i.e., sex, FTCD, DASS-21, and the baseline average value of the corresponding outcome).

Test of Aim 2: The effects of PTBT vs. Control on acute smoking reinforcement (i.e., cigarette purchase task [S-CPT], cigarette satisfaction/reward [mCEQ]) following stress-precipitated smoking will be estimated using separate linear regression models with group predicting each outcome. Planned covariates include the baseline value of the outcome when relevant (S-CPT), biological sex, number of cigarettes per day, and DASS-21, and the models will be tested with and without covariates. Effect size (d) will also be calculated.

Test of Aim 3 (Exploratory Analyses): Differences in CVC (via RSA) between training groups during the stress-precipitated smoking trial will be tested using linear regression models, controlling for baseline levels. Training group will be used to predicting CVC (outcome). Covariates will be identical to those in prior analyses, and will be tested with and without covariates, and effect size (d) will be calculated.

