Participants will be attached to physiological recording equipment throughout the session, including blood pressure volume, ECG, and respiration. When they smoke (in a ventilated smoking room), smoking topographical indices will be recorded using the handheld *Clinical Research Support System* (CReSS micro; described in **C.7**).

Training Conditions: Eligible participants will then be **randomized** to either the PTBT or Control (Sham Training) and informed that the training will be used in V2. **Block randomization** will be used with biological sex (female vs. male) as a blocking variable, as sex is a known factors that influences puff topography and reinforcement.^{36,58,59} Both trainings will be time-matched.

PTBT: PTBT is designed to decrease puff topography influences on smoking reward informed by heart rate variability biofeedback paradigms. Participants will be taught how to puff in a way that may feel different from their usual puffing behavior. Participants will be hooked up to a respiratory band, electrocardiogram (ECG) electrodes, and a blood volume sensor finger cuff (pulse plethysmograph) while seated in a ventilated smoking room. Following a 5-min adaptation period, they will be introduced to a breathing pacer (EZ-Air Plus; Biofeedback Foundation of Europe), which is integrated with the *Thought Technology* biofeedback interface (**Figure 4**), and taught how to use the pacer to guide the pace of their inhalation and exhalation. Participants will be taught to breathe steadily as a white ball (pacer) proceeds up the incline, and exhale as they follow the ball on the decline. They will first practice breathing normally with the pacer to ensure they understand the procedures. Then, participants will smoke following the pacer while using the CReSS micro device for a 5-min phase. To address reinforcement immediacy and intensity, the pacer will be set to a 2 sec inhalation matched with a 2 sec exhalation, for a 4 sec cycle, such that *puffing* maps onto a respiration pace of 15 breathes/min. **This pace should minimize CVC (Figure 2, right).** To address reinforcement reliability, the inter-puff-interval will vary between 4 secs and 30 secs as the experimenter will instruct the participant when to puff. In an adjacent room, the experimenter will be able to monitor real-time displays of physiological data and observe the session via video

Figure 4. Example of Biofeedback Display during PTBT

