1.5 Sample Size Justification

The effects of PTBT on the outcomes of interest are unclear given that there are no prior data. However, our studies of differences in puff topography in the context of acute stress vs. control produce medium-sized effects ($ds=0.46-0.54$).³⁶ Thus, we believe a medium size effect is clinically meaningful, and therefore, the sample size was calculated to detect a medium effect size difference across training groups. **Mean Difference.** For linear regression models, a sample size of 58 is sufficient to detect a medium effect size ($f^2=.143$ [R^2 change/1-cumulative R^2] = .143) with 80% power and alpha of 0.05 via multiple regression analyses with up to 10% variance explained by the main predictor (training group) and up to 5 other covariates (e.g., sex, number of cigarettes per day, depressive/anxiety symptom severity, corresponding baseline values, and CO boost) accounting for up to additional 20% of the anticipated variance. Without any covariates in the model, a sample size of 73 is needed to detect a medium effect size ($f^2=.11$) across training groups (explaining 10% variance). **Mediation (Aim 3).** Statistical power for a mediation analysis with a single mediator was estimated using Monte Carlo power analysis for indirect effects.⁸⁶ The inclusion of mediation analyses led us to increase our sample size to $n=80$, which is sufficient for detection of indirect effects with a proportion-mediated effect size of 50%⁸⁷ (correlations between predictor, mediators, and outcome, $r=.40-.43$) with 80% power and alpha of 0.05. which we deemed sufficient given the exploratory nature of these analyses. **Taken together**, to ensure analyses are adequately powered, we propose a sample of 88 (allowing for ~8-10% attrition) with a final intended sample of 80 completers (40 per condition).

[figure not shown]

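### Each group effect is tested with and without covariates, and in Aim 1 also by two model types, with no version named as deciding

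*Combined protocol and SAP*

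**What the plan says.** Section 6.1 regresses the session mean of each topography index (puff volume, puff duration, inter-puff interval) on training group. The planned covariates are sex, cigarettes per day and DASS-21, "and the models will be tested with and without covariates".

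The same section then fits multilevel models to the individual puffs. Puff number is centred at each person's mid-point, so the intercept is that person's mean level and the group effect on it is again a difference in means. Here, "The models will be fitted with and without level 2 planned covariates", and the covariates are sex, FTCD, DASS-21 and a baseline average of the outcome.

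Aim 2 is also run both ways, adding the baseline S-CPT value where relevant. Aim 3, labelled exploratory, controls for baseline RSA and is otherwise run both ways.

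On allocation, section 1.3 says that block randomization "will be used with biological sex (female vs. male) as a blocking variable". On size, section 1.5 covers both versions: "a sample size of 58 is sufficient to detect a medium effect size" with covariates, and "Without any covariates in the model, a sample size of 73 is needed to detect a medium effect size". Neither section calls one version primary or the other a sensitivity analysis, or says what follows if they disagree.

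**The concern.** Section 1.1 states directional hypotheses of significant differences, and section 1.5 sets alpha at 0.05. A decision rule is therefore intended, but it is incomplete. Three things are at stake:

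- **Error rate.** If a significant result from either version may be cited, the error rate exceeds 0.05.
- **Disagreement.** If the versions differ, the plan gives no answer.
- **Efficiency.** If the unadjusted version is relied on, it discards sex, which was important enough to block on, along with baseline measures already collected.

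Aim 1 is the most open. Two model types, each run two ways with different covariate sets, bear on one mean difference per index.

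**Working it through.** **1. The plan's own figures.** For a 1-df group effect, power comes from the noncentral F distribution with λ = f²N and N − k − 1 denominator df, where k is the number of predictors. Section 1.5 gives "with 80% power and alpha of 0.05 via multiple regression analyses", a group effect explaining 10% of variance, and up to five covariates "accounting for up to additional 20% of the anticipated variance".

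- With covariates: f² = .10/(1 − .30) = .143 and k = 6. N = 58 gives 80.7% power, so 58 reproduces.
- Without: f² = .10/.90 = .111 and k = 1. N = 73 gives 80.2%, so 73 reproduces.
- At 80 completers the same effects give about 92% and 84%. Both versions clear the 80% target, so the sample size does not choose between them.

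**2. Type I error if either regression may count.** The inputs were 80 completers, 40 per arm, sex exactly balanced by arm (an idealization of the blocking), 3 or 5 covariates, and 40,000 simulated null trials per setting. The variance explained by the covariates is an assumption up to the plan's 20% ceiling, and beyond it in the last row.

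| Covariate R² | Unadjusted | Adjusted | Either |
|---|---|---|---|
| .10 | 4.5-4.7% | 4.9% | 6.2% |
| .20 | 4.4-4.5% | 4.9-5.1% | 6.5-6.9% |
| .40 | 3.7-3.8% | 5.0% | 6.8-6.9% |

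A separate simulation, also with sex balanced by arm, gave 6.2-6.5% for the either-model rate, so about 6-7% is a fair summary. Two independent tests would give 1 − .95² = 9.75%; the two versions are strongly correlated, so the rate stays well below that.

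**3. Any of the three topography indices.** For moderately correlated indices (assumed about .3 to .4), one model per index gives about 13-14% for at least one false positive. Allowing either model gives about 16-17%. Dual testing therefore adds about 3 points; the rest comes from testing three outcomes.

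**4. Disagreement.** With a true difference of 0.50 SD and covariate R² = .20 (both assumed), 71.0% of simulated trials were significant in at least one version and 56.6% in both. The difference, 71.0 − 56.6 = 14.4%, is the share in which they disagree. At R² = .40 it is about 24%. Under the null with R² = .20 it is 3.5-4%.

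**5. Omitting sex.** Balancing sex by design and then leaving it out of the model overstates the standard error. If sex alone explained 10% or 20% of outcome variance (assumed), the unadjusted test would reject in about 3.7% or 2.9% of null trials. The omission costs power and does not add false positives.

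**6. Power at d = 0.50 and N = 80.** Unadjusted: f² = d²/4 = .0625, k = 1, power 60%. Adjusted with three covariates: f² = .0625/(1 − R²), k = 4.

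| Covariate R² | f² | Power |
|---|---|---|
| .05 | .0658 | 62% |
| .10 | .0694 | 64% |
| .20 | .0781 | 69% |

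The last row is a ceiling. The plan's 20% is an upper limit for up to five covariates, which include baseline outcome values and CO boost; sex, cigarettes per day and DASS-21 alone may explain less. Simulation at R² = .20 gives 68%, because chance covariate imbalance costs a little.

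**The case against.** Running both versions can be read as transparent sensitivity analysis. The study is a proof of concept, Aim 3 is exploratory, and no sentence says that either p-value suffices. The adjusted model, with sex in it, is already planned in every aim. Aim 3 already adjusts for baseline RSA. At the effect the plan sizes for, both versions have more than 80% power.

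All of this is correct, and it limits the size of the point. The error inflation is conditional on how the results are used, and amounts to 1-2 percentage points per outcome. But a sensitivity analysis needs a main analysis to be compared with, and none is named. The disagreement problem remains however honestly both results are reported.

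Three stronger readings are tempting and are not supported:

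- Two tests nearly double the error rate. They do not, because they are highly correlated.
- Leaving out the blocking factor raises false positives. It does the opposite.
- The 16-17% chance of a false positive among the three indices is due to the covariate wording. Most of it would be there with a single model.

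**Conclusion.** The point stands as a gap worth closing, of modest size. Section 6.1 names no deciding version in any aim, and Aim 1 leaves up to four p-values per index for one mean difference.

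If either regression may count, type I error is about 6-7% per outcome (covariate R² of 10-20%). The four-way choice in Aim 1 was not simulated. The clearer practical risk is conflicting answers, in about one trial in seven at d = 0.50 and R² = .20. Choosing the adjusted version gains about 2 to 9 points of power at d = 0.50, depending on what the covariates explain. The effect size, the covariate R² and the correlation between indices are assumptions; the plan gives only an upper limit for R².

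**What to change.** In section 6.1:

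- **Aim 1.** For each index, the linear regression of the session mean adjusted for sex, cigarettes per day and DASS-21 decides. The multilevel models address the trajectory question and use the same covariates. Merely saying that the adjusted model decides would leave two deciding tests per index.
- **Baseline topography.** Do not adjust for V1 topography if it was recorded during the assigned training. Section 1.3 places randomization before the V1 training cigarette, so such a value would be affected by the randomized condition. If a recording made before randomization exists, say so and define it.
- **Aim 2.** The adjusted model decides, with an S-CPT value measured before randomization added for the S-CPT outcomes. The remote-session value qualifies.
- **Aim 3.** The sex-adjusted model, with the baseline RSA already planned, is the main exploratory analysis.
- **All aims.** Unadjusted models are reported as sensitivity analyses.

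This takes a few sentences and no new data. It uses three residual degrees of freedom of the 78 in the unadjusted model, or four where a baseline value is added. It does not deal with multiplicity across the three indices, which is a separate matter.
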